4. SUBJECT DISPOSITION

4.1. Subject Enrollment and Disposition

A summary of subject enrollment will be provided by treatment group for each country within each geographic region, and investigator within a country. The summary will present the number and percentage of subjects enrolled. For each column, the denominator for the percentage calculation will be the total number of subjects analyzed for that column.

The randomization schedule used for the study will be provided in a listing and used as an appendix to the CSR.

A summary of subject disposition will be provided by treatment group. This summary will present the number of subjects in each of the categories listed below:

- Safety Analysis Set
- Full Analysis Set
- Continuing study
- Completed study
- Did not complete study with reasons for premature discontinuation from the study

For the status of study completion and reasons for premature discontinuation, the number and percentage of subjects in each category will be provided. The denominator for the percentage calculation will be the total number of subjects in the Safety Analysis Set corresponding to that column.

A by-subject listing of reasons for premature study discontinuation will be provided by subject identification (ID) number in ascending order to support the above summary tables.

4.2. Extent of Filgotinib Exposure

Total duration of exposure to filgotinib will be defined as (last dose date of filgotinib in GLPG0634-CL-205 - first dose date of filgotinib in the core studies or GLPG0634-CL-205 + 1), regardless of any temporary interruptions in administration and will be expressed in weeks using up to 1 decimal place (eg, 4.5 weeks).

If the last filgotinib dosing date is missing, the latest date among the clinical visit date and laboratory sample collection date that occurred during the on-treatment period will be used.

If subjects are continuing on study drug, The data cutoff date will be used to impute the last dosing date for the calculation of the duration of exposure to filgotinib.

The total duration of exposure to filgotinib will be summarized using descriptive statistics and using the number (ie, cumulative counts) and percentage of subjects exposed for filgotinib baseline and every 12 weeks afterwards.

Summaries will be provided by treatment group for the Safety Analysis Set. No formal statistical testing is planned.

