- 2 sequential decreases from the baseline (of the core studies [GLPG0634-CL-203 or GLPG0634-CL-204]) of inhibin B by 50% with clinically relevant concurrent increase in FSH^c per investigator judgment. Note that this study drug discontinuation criterion applies only to subjects with baseline hormone levels within normal limits;
- 2 sequential decreases from the baseline (of the core studies [GLPG0634-CL-203 or GLPG0634-CL-204]) of testosterone by 50% with clinically relevant concurrent increase in LH, per investigator judgment^c. Note that this study drug discontinuation criterion applies only to subjects with baseline hormone levels within normal limits.

^a In each case, there is a need for additional investigations, such as review of ethanol, recreational drug and dietary supplement consumption; testing for acute hepatitis A, B or C infection and biliary tract imaging should be promptly discussed with the medical monitor.

^b If Creatinine Clearance has not been centrally reported, use the following: 2 sequential increases in serum creatinine >50% over the averaged of screening and baseline value (of the core studies [GLPG0634-CL-203 or GLPG0634-CL-204]).

^c In each case, hormones in male subjects should be monitored monthly and if no positive dynamics is seen after 3 months from stopping filgotinib, referral to an andrologist should be considered.

Subjects withdrawing from the study will be encouraged to complete the same final evaluations as subjects completing the study according to the protocol (please refer to Section 8.7.2.3 Final Visit or EDV), particularly safety evaluations in the subject's interest. The aim is to record data in the same way as for subjects who completed the study. Subjects are free to withdraw from the study at any time without providing reason(s) for withdrawal and without prejudice to further treatment. The reason(s) for withdrawal will be documented in the electronic case report form (eCRF).

Reasonable efforts will be made to contact subjects who are lost to follow-up. These must be documented in the subject's file.

The sponsor has the right to terminate the study at any time in case of safety concerns or if special circumstances concerning the study medication or the company itself occur, making further treatment of subjects impossible. In this event, the investigator(s) and relevant authorities will be informed of the reason for study termination.

The medical monitor should consult the medical leader as needed.

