In case of temperature excursions (outside the permitted range mentioned above), the sponsor should immediately be contacted for evaluation of the excursion and further use of the study drug.

Until dispensed to the subjects, all drug products should be stored in a securely locked area, accessible only to authorized site personnel. To ensure the stability of the study drug and to ensure proper product identification, the drug product should not be stored in a container other than the container in which it is supplied.

Consideration should be given to handling, preparation, and disposal through measures that minimize drug contact with the body. Appropriate precautions should be followed to avoid direct eye contact or exposure when handling.

8.6.4 **Method of Assigning Subjects to Treatment Groups**

Following completion of one of the previous core studies (GLPG0634-CL-203 or GLPG0634-CL-204), subjects who are deemed by the investigator to benefit from continued therapy with study medication, will be offered the option to enter this Long-term Follow-up study. All subjects who opt to roll over into this study will be enrolled and will start the study at the same dose (filgotinib 200 mg daily, administered as either 200 mg q.d. or as 100 mg b.i.d., depending on the q.d./b.i.d. regimen of the preceding core study). Subjects who were on 24 weeks of placebo during the core study

GLPG0634-CL-203 will be randomly assigned to either 100 mg b.i.d. or 200 mg q.d. All other subjects will switch to 200 mg daily, keeping the same regimen (q.d. or b.i.d.) they had in the preceding core study.

This will be done according to a pre-specified randomization scheme prepared by an independent statistician within [REDACTED]. Upon qualification for the study, subjects will be randomized using a computerized interactive voice/web response system (IXRS) [REDACTED] to filgotinib 200 mg q.d. or 100 mg b.i.d. in a 1:1 ratio.

For each subject at each visit, the clinic will contact the IXRS system and will be given the appropriate kit number to be dispensed. The kit will contain the relevant study medication until the next visit.

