3.3. Missing Data and Outliers

3.3.1. Missing Data

In general, missing data will not be imputed unless methods for handling missing data are specified. Exceptions are presented in this document.

For missing last dosing date of study drug, imputation rules are described in Section 4.2. For partial date of initial RA diagnosis, imputation rules are described in Section 5.2. The handling of missing or incomplete dates for AE onset is described in Section 7.1.5.2. The handling of missing or incomplete dates for prior medications is described in Section 5.2. and for concomitant medications in Section 7.4. Imputation rules adopted in the efficacy analyses are specified in Section 6.1.

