3.5. Analysis Visit Window

3.5.1. Definition of Study Day

The first dose date of individual study drug will be calculated separately for each study drug in a treatment group. Study Day 1 is defined as the first dose date of any study drug, which is the minimum of the first dose dates of individual study drugs in a treatment group.

The last dose date of individual study drug will be calculated separately for each study drug in a treatment group. The last dose date of any study drug will be defined as the maximum of the last dose dates of individual study drugs in a treatment group.

The first dose date of individual study drug in GLPG0634-CL-205 is identified by the first drug dispense date + 1 day. The last dose date of individual study drug in GLPG0634-CL-205 is identified by the Final Visit date or the Early Discontinuation Visit date.

Study Day will be calculated from the Reference Date and derived as follows:

- For postdose study days: Assessment date – Reference Date + 1
- For days prior to the first dose: Assessment date – Reference Date

Reference Date is defined as follows:

- For efficacy data in the core studies: Study Day 1 in the core studies
- For efficacy data in GLPG0634-CL-205: Study Day 1 in GLPG0634-CL-205
- For safety data: The first dose date of filgotinib in the core studies or GLPG0634-CL-205

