7.1.5. Treatment-Emergent Adverse Events

7.1.5.1. Definition of Treatment-Emergent Adverse Events

Treatment-emergent adverse events (TEAEs) are defined as any AEs with an onset date on or after the filgotinib start date in the core studies or GLPG0634-CL-205, and no later than 30 days after permanent discontinuation of filgotinib in GLPG0634-CL-205.

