7.1.5.2. Incomplete Dates

If the onset date of the AE is incomplete and the AE stop date is not prior to the first dosing date of filgotinib in the core studies or GLPG0634-CL-205, then the month and year (or year alone if month is not recorded) of onset determine whether an AE is treatment emergent. The event is considered treatment emergent if both of the following 2 criteria are met:

- The AE onset is the same as or after the month and year (or year) of the first dosing date of filgotinib in the core studies or GLPG0634-CL-205, and
- The AE onset date is the same as or before the month and year (or year) of the date corresponding to 30 days after the date of the last dose of filgotinib in GLPG0634-CL-205

An AE with completely missing onset and stop dates, or with the onset date missing and a stop date later than the first dosing date of filgotinib in the core studies or GLPG0634-CL-205, will be considered to be treatment emergent. In addition, an AE with the onset date missing and incomplete stop date with the same or later month and year (or year alone if month is not recorded) as the first dosing date of filgotinib in the core studies or GLPG0634-CL-205 will be considered treatment emergent.

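### For a subject with no Final Visit or EDV, the SAP ends filgotinib at the last visit or sample although about 84 days of drug had been dispensed, so on-drug events starting more than 30 days later can miss the treatment-emergent tables

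*SAP*

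**What the plan says.** **Last dose date.** SAP 3.5.1: "The last dose date of individual study drug in GLPG0634-CL-205 is identified by the Final Visit date or the Early Discontinuation Visit date". It names no intake record, tablet return, stop date or date of death as a source.

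**When it is missing.** SAP 3.3.1, the general section on missing data, refers on: "For missing last dosing date of study drug, imputation rules are described in Section 4.2". The rule is therefore not confined to the exposure table. SAP 4.2 then states that "the latest date among the clinical visit date and laboratory sample collection date that occurred during the on-treatment period will be used". A separate sentence there uses the data cutoff date for subjects still on drug. Neither sentence mentions death.

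**Treatment-emergent window.** SAP 7.1.5.1 requires onset "no later than 30 days after permanent discontinuation of filgotinib in GLPG0634-CL-205". SAP 7.1.5.2, for incomplete onset dates, sets the upper limit by "the date corresponding to 30 days after the date of the last dose of filgotinib in GLPG0634-CL-205".

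**Supply and visits.** Protocol 8.6.4: "The kit will contain the relevant study medication until the next visit". Protocol 8.7.2.1 places quarterly visits 12 weeks apart, each within 1 week of a day counted from the start of intake.

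**Attendance at the EDV.** Protocol 8.1 and 8.7.4 provide for an EDV after early withdrawal. Protocol 8.4.2 puts attendance more softly: "Subjects withdrawing from the study will be encouraged to complete the same final evaluations as subjects completing the study".

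**The concern.** The imputed last dose will often be the day on which the subject was handed the next 12 weeks of tablets. The rule treats the subject as having stopped on the day of resupply. A subject who dies before the next visit cannot attend an EDV, so this is the rule that applies to that subject.

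Long-term safety is the primary objective, and the error runs in the drug's favour. It also goes against the SAP's other choices:

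- In 4.2, a continuing subject is credited with drug up to the data cutoff without needing a visit on that date.
- Missing causality counts as related (7.1.3).
- Completely missing event dates count as treatment-emergent (7.1.5.2).
- A graded laboratory abnormality with no baseline counts as treatment-emergent (7.2.2.1).

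Two smaller problems follow. The imputation searches within an on-treatment period that the SAP does not define, and whose natural end is the very date that is missing. And SAP 7.4 drops medications started after the last dosing date, so treatment given for a late terminal event can leave the concomitant medication summary.

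**Working it through.** The plan gives no figure on this point, so there is none to reproduce. The check is date arithmetic.

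**Inputs**

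- V: the latest on-treatment visit or laboratory date, taken as the last quarterly visit (SAP 4.2).
- L: days of drug dispensed at V, equal to the gap to the next visit (Protocol 8.6.4). Nominally 12 × 7 = 84 days. Visits are timed from the start of intake, so two neighbouring visits can each be off by 7 days, and L runs from 84 − 14 = 70 to 84 + 14 = 98.
- Window: 30 days (SAP 7.1.5).

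**Step 1: the date used.** No Final Visit or EDV means no last dose date under 3.5.1. SAP 3.3.1 sends this to 4.2, and 4.2 returns V.

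**Step 2: the window.** SAP 7.1.5.2 counts from the last dose, so the window closes at V + 30. SAP 7.1.5.1 counts from permanent discontinuation and does not define that date. The laboratory rules in 7.2 and 7.2.2.1 use last dose plus 30 days for subjects who have permanently discontinued, which suggests that the two are meant to be the same date.

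**Step 3: supplied days outside the window** = L − 30; share = (L − 30)/L.

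| L (days) | Outside the window | Share |
|---|---|---|
| 70 | 40 | 57% |
| 77 | 47 | 61% |
| 84 | 54 | 64% |
| 91 | 61 | 67% |
| 98 | 68 | 69% |

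If the true last dose was at V + d, the window should close at V + d + 30. For d = 42 that is V + 72, and for d = 84 it is V + 114. The SAP rule closes it at V + 30 in both cases.

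**Step 4: exposure.** If drug was in fact taken to a point uniformly distributed over the 84 days, the mean understatement is 84/2 = 42 days, or 42/365.25 = 0.115 patient-years per affected subject.

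**Step 5: illustration.** The documents do not say how many subjects lack both visits. Assume 10, 30 or 60, each with one event uniformly placed over the 84 days:

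- Events outside the window: 10 × 54/84 = 6.4; 30 × 54/84 = 19.3; 60 × 54/84 = 38.6.
- Patient-years not counted: 1.15, 3.45 and 6.90.

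**Step 6: outputs affected.** In SAP 7.1.6.1 the summaries of TE SAEs, TE SAEs with a fatal outcome, severe TEAEs and related TEAEs depend on the flag. The count of all deaths in the high-level summary does not. Nor do the listings of all AEs (with the flag shown), SAEs and deaths. The MACE summary (7.1.7.1) and the special-interest summaries (7.1.7.2) are not expressly limited to treatment-emergent events.

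**The case against.** **The main window definition does not name the imputed date.** SAP 7.1.5.1 speaks of permanent discontinuation, and 7.1.5.2 applies only to incomplete onset dates. A subject who dies on drug could be said to discontinue at death, and the event would then count. This stands as a limit: the SAP can be read either way. It does not remove the problem, because the only last-dose rules in the SAP lead to V, and no other source for the date is named.

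**Not everyone without an EDV was still on drug.** A reader might infer that losses to follow-up and refusals are affected just as deaths are. The documents do not support that. Subjects lost to follow-up generally report no later events, and whether those who refuse a visit kept dosing is unknown. The premise is firm mainly for deaths and terminal events between visits.

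**The 64% is conditional.** Status depends on onset: an illness that begins within 30 days of V and is fatal later still counts. Unscheduled visits (Protocol 8.1) and laboratory retests (Protocol 8.4.2) move the imputed date forward. Both points stand.

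**Fatal events stay visible.** A reader might infer that deaths vanish from the report, or that the all-deaths count and the fatal TE SAE count must disagree. Neither follows. Step 6 shows where such events remain, and no actual case is known. What stands is narrower: a listing does not correct an incidence table.

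**The exposure effect is small for long stayers.** Against about 96 months (96 × 30.44 ≈ 2,922 days), 42 days is 42/2,922 = 1.4%. That is fair, though the share is larger for early leavers and does not bear on whether an event is counted.

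**Conclusion.** The rule is wrong as written and should be fixed. For a subject with no Final Visit or EDV, the SAP places the last dose at the latest on-treatment visit or sample while dispensed drug remains. On the 7.1.5.2 reading of the window, on-drug events starting more than 30 days after that date are misclassified as not treatment-emergent. The uncovered share of the supply is 64% (57% to 69% over the permitted visit gaps). As a share of events, it rests on uniform onset, continued dosing and no later visit or sample.

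The direction is to understate harm in the main TEAE tables. The absolute size cannot be given, because the number of affected subjects is not stated and may be small. The study is descriptive with no formal testing, so no test result is at risk. The documents do not support a claim that the safety report as a whole conceals deaths.

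**What to change.** In SAP 4.2 and 7.1.5, add a rule for subjects with no Final Visit or EDV:

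1. Set the last dose date to the recorded last intake or stop date if there is one. Otherwise use the earlier of the date of death and the end of the dispensed supply (next scheduled visit).
2. State that 7.1.5.1 and 7.1.5.2 both use this date plus 30 days, which also settles what permanent discontinuation means.
3. Use the same date for duration of exposure, so that events and exposure match in any patient-year analysis (allowed by Protocol 8.9.1.3).
4. Define the on-treatment period without reference to the missing date.

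No separate laboratory window is needed, since a later on-treatment sample already moves the imputed date. No new listing is needed, since 7.1.6.1 already lists all AEs with the flag, and SAEs and deaths.

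The cost is a few lines of SAP text and one derived date, with no new data collection. The downside is that a few events in subjects who stopped soon after their last visit will count as treatment-emergent, which is conservative for safety. The change belongs before database finalization; after SAP finalization it would have to be documented in the CSR, as SAP section 1 requires.

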4.3. Protocol Deviations

Subjects who did not meet the eligibility criteria for study entry, but enrolled in the study will be summarized regardless of whether they were exempted by the sponsor or not. The summary will present the number and percentage of subjects who did not meet at least 1 eligibility criterion and the number of subjects who did not meet specific criteria by treatment group based on the Safety Analysis Set. A by-subject listing will be provided for those subjects who did not meet at least 1 eligibility (inclusion or exclusion) criterion. The listing will present the eligibility criterion (or criteria if more than 1 deviation) that subjects did not meet and related comments, if collected.

Protocol deviations occurring after subjects entered the study are documented during routine monitoring. The number and percentage of subjects with important protocol deviations by deviation reason (eg, nonadherence to study drug, violation of select inclusion/exclusion criteria) will be summarized by treatment group for the Safety Analysis Set. A by-subject listing will be provided for those subjects with important protocol deviation.

5. BASELINE CHARACTERISTICS

5.1. Demographics and Other Core Baseline Characteristics

Subject demographic and other core baseline characteristics variables will be summarized by treatment group and overall using descriptive statistics for continuous variables, and using number and percentage of subjects for categorical variables. The summary of demographic and other core baseline characteristics data will be provided for the Safety Analysis Set for the following:

- Age (on the first dose date of any study drug in the core studies)
- Sex at birth (male, female)
- Race
- Ethnicity (Hispanic or Latino, not Hispanic or Latino)
- Geographic region and country (Region 1: Latin America; Region 2: Central and Eastern Europe, EU; Region 3: Central and Eastern Europe, non-EU; Region 4: West and Asia Pac)
- Weight (kg)
- Height (cm)
- Body mass index (BMI; in kg/m^2)

A by-subject demographic and other core baseline characteristics listing, including the informed consent date, will be provided by subject ID number in ascending order.

5.2. Core Baseline Disease Characteristics

Core baseline disease characteristics include:

- Duration from RA diagnosis (years)

Calculated as $((\text{first dose date of study drug in the core studies}) - (\text{date of initial diagnosis}) + 1 \text{ day}) / 365.25$. If the date of initial diagnosis is incomplete, then the following rules will be applied:

— missing day: use the first of the month

— missing month: use January

- Presence of RF (Yes/No)

Positive presence of RF is defined as RF value $>$ ULN

- Presence of anti-CCP (Yes/No)

Positive presence of anti-CCP is defined as anti-CCP value > ULN

- Prior exposure to bDMARDs (Yes/No)

Prior exposure to bDMARDs (Please refer to [Appendix 1](#) for a list of bDMARDs) are defined as any bDMARDs taken before a subject took the first study drug in the core studies. A subject reporting the same bDMARDs more than once will be counted only once when calculating the number and percentage of subjects who received bDMARDs.

For the purposes of analysis, any bDMARDs with a start date prior to the first dosing date of any study drug in the core studies will be counted regardless of when the stop date is. If a partial start date is entered the bDMARDs will be considered prior unless the month and year (if day is missing) or year (if day and month are missing) of the start date are after the first dosing date in the core studies. bDMARDs with a completely missing start date will be counted, unless otherwise specified.

- Concurrent oral corticosteroids use on the first dosing date (Yes/No)

— Oral corticosteroids dose, mg/day, expressed as prednisone-equivalent dose, mean (SD)

- Concurrent MTX use on the first dosing date (Yes/No)

— MTX dose, mg/week, mean (SD)

These core baseline disease characteristics will be summarized by treatment group and overall using descriptive statistics for continuous variables and using number and percentage of subjects for categorical variables. The summary of core baseline characteristics will be provided for the Safety Analysis Set.

A by-subject listing of core baseline disease characteristics will be provided by subject ID number in ascending order.

